17 VULNERABLE POPULATIONS

N/A

18 COMMUNITY-BASED PARTICIPATORY RESEARCH

N/A

19 SHARING OF RESULTS WITH SUBJECTS

N/A

20 SETTING

The potential subjects will be identified in the genitourinary clinic at Roswell Park Comprehensive Cancer Center where they will meet with one of the research team members and in the inpatient wards. The research procedure will be performed at Roswell Park Comprehensive Cancer Center inpatient wards.

21 PROVISIONS TO PROTECT THE PRIVACY INTERESTS OF SUBJECTS

Participants will be free to determine whether to respond to requests for participation. All participants, even after providing consent, are free not to answer any questions, or choose to end their participation and thus can privately maintain control over the level of information provided to us. No PHI will be recorded.

Data will be stored on a secured, password protected RPCI server in the Urology department that is maintained by the information technology department. Access will be limited to the PI and Coinvestigator's.

22 RESOURCES AVAILABLE

Our research team comprises of surgeons, clinical and research fellows, research assistants and coordinators. Our diverse team has worked on similar projects and has extensive experience in undergoing clinical trials. [name] laboratory, the Advanced Technologies Laboratory for Advanced Surgery (ATLAS) is located at Grace Cancer Drug Center is approximately 1400 sq. feet. A major portion of the lab is dedicated for industrial and human factor engineering researches and sciences. The laboratory is fully equipped to safely carry out and develop the proposed work. The laboratory personnel comprised of surgeons, clinical and research fellows, medical illustrators and engineers are highly experienced in conducting clinical research. The innovative multidisciplinary team utilizes the lab space for equipment storage and

PROTOCOL TITLE: Does increased mobility assessed with 3D motion tracking technology lead to early post-operative recovery among patients undergoing oncologic surgeries

data analysis. Space and network access are readily available throughout the study period. The PI, [name], and the research team members have their dedicated equipped work space with secretarial support. All participating research members will receive an in-service that adequately explains the research protocol, procedures and individual duties.

23 PRIOR APPROVALS

N/A

24 ECONOMIC BURDEN TO SUBJECTS

There are no costs to the subjects.

25 CONSENT PROCESS

This study will not be initiated until the protocol and informed consent document(s) have been reviewed and approved by a properly constituted Institutional Review Board (IRB) or Independent Ethics Committee (IEC). Each participant (or legal guardian) shall read, understand, APPROVED RPCI IRB Protocol and sign an instrument of informed consent prior to performance of any study-specific procedure. It is the responsibility of the investigator to ensure that the participant is made aware of the investigational nature of the treatment and that informed consent is given. The Investigator is responsible for the retention of the participant log and participant records; although personal information may be reviewed by authorized persons, that information will be treated as strictly confidential and will not be made publicly available. The investigator is also responsible for obtaining participant authorization to access medical records and other applicable study specific information according to Health Insurance Portability and Accountability Act regulations (where applicable). This study will be conducted in compliance with all applicable laws and regulations of the state and/or country and institution where the participant is treated. The clinical trial should be conducted in accordance with the ethical principles embodied in the Belmont Report: Ethical Principles and Guidelines for the Protection of Human Subjects of Research, consistent with good clinical practice and the applicable regulatory requirements and according to the guidelines in this protocol, including attached appendices. The RPCI SOP: Informed Consent Process for Research (HRP-090) will be followed.

This study will be conducted in compliance with all applicable laws and regulations of the state and/or country and institution where the participant is treated. The clinical trial should be conducted in accordance with the ethical principles embodied in the Belmont Report: Ethical Principles and Guidelines for the Protection of Human Subjects of Research, consistent with good clinical practice and the applicable regulatory requirements and according to the guidelines in this protocol, including attached appendices.

26 PROCESS TO DOCUMENT CONSENT IN WRITING

The Investigator (or IRB specified designee) is responsible for obtaining written consent from each participant or the participant's legally authorized representative in accordance with GCP guidelines using the approved informed consent form, before any study specific procedures (including screening procedures) are performed. The informed consent form acknowledges all information that must be given to the participant according to applicable GCP guidelines, including the purpose and nature of the study, the expected efficacy and possible side effects of

PROTOCOL TITLE: Does increased mobility assessed with 3D motion tracking technology lead to early post-operative recovery among patients undergoing oncologic surgeries

the treatment(s), and specifying that refusal to participate will not influence further options for therapy. Any additional information that is applicable to the study must also be included. Additional national or institutionally mandated requirements for informed consent must also be adhered to. The participant should also be made aware that by signing the consent form, processing of sensitive clinical trial data and transfer to other countries for further processing is allowed. The Investigator shall provide a copy of the signed consent form to the participant and the signed original shall be maintained in the Investigator File. A copy of the signed consent form must be filed in the participant file. At any stage, the participant may withdraw from the study and such a decision will not affect any further treatment options. The RPCC “SOP: Written Documentation of Consent (HRP-091)” will be followed.

27 DRUGS OR DEVICES

3D motion tracking system (Xsens) is commercially available device used in research, especially sport medicine. These devices will not be used for any off label purposes. They will be stored in the ATLAS lab (G-401).

PROTOCOL TITLE: Does increased mobility assessed with 3D motion tracking technology lead to early post-operative recovery among patients undergoing oncologic surgeries

29 APPENDICES/ SUPPLEMENTS

PROTOCOL TITLE: Does increased mobility assessed with 3D motion tracking technology lead to early post-operative recovery among patients undergoing oncologic surgeries

Appendix A:

Xsens Motion Tracking Technology

PROTOCOL TITLE: Does increased mobility assessed with 3D motion tracking technology lead to early post-operative recovery among patients undergoing oncologic surgeries

Appendix B.

Post study questionnaire documenting postoperative problems from the perspective of the patient and study feedback

Post Experiment Questionnaire

Participant ID:

Date of Surgery:

Date of Questionnaire Completion:

How satisfied were you with the process of applying of sensors?

Very Unsatisfied	Unsatisfied	Neutral	Satisfied	Very Satisfied
------------------	-------------	---------	-----------	----------------

Were the sensors comfortable throughout your wear?

Very Uncomfortable	Uncomfortable	Neutral	Comfortable	Very Comfortable
--------------------	---------------	---------	-------------	------------------

Did having the sensors on push you to walk more?

Very Unlikely	Unlikely	Neutral	Likely	Very Likely
---------------	----------	---------	--------	-------------

How much of your previous mobility have you regained since the operation?

0%	25%	50%	75%	100%
----	-----	-----	-----	------

Have you been pushing yourself to exercise since the operation?

Never	Rarely	Sometimes	Often	Always
-------	--------	-----------	-------	--------

How Much Pain Do You Feel Day to Day?

Not At All	A Little Bit	Moderately	Quite A Bit	Extremely
------------	--------------	------------	-------------	-----------

Your quality of life now compared to the month before the surgery?

A lot worse	Somewhat Worse	About the Same	Somewhat Better	A Lot Better
-------------	----------------	----------------	-----------------	--------------

How Do You Feel About Yourself as A Result Of Your Surgery?

A lot worse	Somewhat Worse	About the Same	Somewhat Better	A Lot Better
-------------	----------------	----------------	-----------------	--------------

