8 STUDY ENDPOINTS

The primary study endpoint is measuring early recovery of postoperative course by calculating early return of bowel motion (passing flatus and/or stool on which postoperative day), presence or absence of nausea and/or vomiting, presence or absence of chest symptoms (cough, sputum

PROTOCOL TITLE: Does increased mobility assessed with 3D motion tracking technology lead to early post-operative recovery among patients undergoing oncologic surgeries

and ability of using incentive spirometry), early discharge from the hospital and 30 days surgical related complications and readmissions.

The secondary study endpoint is measuring the range of joint movement in upper and lower joints of body, using the 3D motion tracking system (Xsens), to identify the minimum required level of mobility for better early postoperative course recovery.

A few other secondary endpoints concluded from the post experiment questionnaire include: assessing encouraged walking in the hospital setting subjectively improves their exercise habit outside of the hospital, how was the application of the sensors in a hospital setting as this is the first study to do so, and to assess the subjective impact of complications on quality of life.

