9 PROCEDURES INVOLVED

This is a prospective randomized controlled trial comparing the early postoperative course of patients who undergo inpatient oncological procedures after assessment of their baseline physical activity before the surgery, using validated questionnaires in the clinic, to have a homogenized sample for the study. Participants will be randomized to the control arm (40 participants) and intervention group (40 participants). Control group participants will be asked to walk one to two laps around the ward twice per day, on the first day after the surgery following the usual clinical practice at Roswell Park Comprehensive Cancer Center-urology department (RPCCC). Their movement will be tracked with 3D motion tracking system (Xsens). The intervention arm participants will be asked to walk for minimum 30 minutes per day and their movement also will be tracked with Xsens. In both arms the patients will be asked to mobilize (walk out of the bed) on first day post-surgery under supervision and assistant of attending nurse in the floor if their clinical situation allowed. If patient cannot complete the walking tasks, they will be excluded from the study and they will be replaced by recruiting other patients.

Xsens is a wireless technology that makes use of sensors. The sensors are applied in a non-invasive manner and do not require the suit to be applied. There are various configurations of the sensors that can be utilized. The minimum number of sensors needed is 7. They are applied by using Velcro bands. The entire set-up takes about 5-10 minutes.

The study duration is 24 months or until target accrual is reached. In both arms their mobility will be tracked till they discharged from the hospital. In both arms we will assess the symptoms and signs of gastro-intestinal complications (nausea, vomiting, abdominal pain, passing flatus or stool) and chest symptoms (coughing, sputum, utilizing incentive spirometry) until they are discharged from the hospital. We will continue to follow them for 30 days post discharge to note any complications or readmission.

Patients at standard follow ups, 2 weeks, 6 weeks, 3 months or over the phone will complete a short post study questionnaire (Appendix B). The last three questions are taken from Woodfield et al., who assessed postoperative problems from the perspective of the patient on the identification of complications after surgery (11).

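### The only exercise item in the questionnaire starts its recall period at the operation, so the endpoint on exercise outside hospital can partly reflect the assigned ward walking

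*Combined protocol and SAP*

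**What the plan says.** Section 8 (Study Endpoints) introduces a group of outcomes with "A few other secondary endpoints concluded from the post experiment questionnaire include". The first of them is "assessing encouraged walking in the hospital setting subjectively improves their exercise habit outside of the hospital".

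The questionnaire in Appendix B has eight items. One concerns exercise: "Have you been pushing yourself to exercise since the operation", answered on a five-point scale from Never to Always. Two others come near the subject. One is "Did having the sensors on push you to walk more" and the other is "How much of your previous mobility have you regained since the operation".

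Section 9 (Procedures Involved) gives the assigned walking. For the intervention arm: "The intervention arm participants will be asked to walk for minimum 30 minutes per day". For the control arm: "Control group participants will be asked to walk one to two laps around the ward twice per day". Both arms begin on the first day after surgery, and the sensors track movement until discharge.

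Sections 7 and 9 have the questionnaire completed at a follow-up visit 2 weeks, 6 weeks or 3 months after discharge, or by phone. No single time is fixed. Section 16 (Statistical Plan) contains no analysis of any questionnaire item.

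**The concern.** The endpoint concerns what patients do after they leave hospital, but the item's recall period opens at the operation. It therefore takes in the days on which the randomised treatment was given. A patient in the intervention arm who walked as asked on the ward and did little at home could truthfully give a middling or high answer. Section 9 also excludes and replaces patients who cannot complete the walking tasks, so those who remain in the intervention arm are mostly people who did the assigned walking.

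If the arms differ on this item, a reader could not tell whether habits after discharge changed or whether patients were reporting the intervention itself. Later analysis cannot repair this. Appendix B records the dates of surgery and of completion, so with the discharge date the length of the inpatient period can be worked out for each patient. How much of the answer refers to that period cannot.

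**Working it through.** **The plan's own figure.** The only calculation in the documents (Sample Size Determination in section 16) concerns a mobility measure: 40 per group, two-sided 0.05, a difference of 0.63 SD, 80% power. It reproduces: 0.63 × √(40/2) = 2.817, and Φ(2.817 − 1.960) = 80.4%. The exact t calculation with 78 degrees of freedom gives 79.5%. It has no bearing on the questionnaire item, for which the plan gives no figure.

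**Does any other item measure exercise after discharge?**

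| Appendix B item | Subject | Period covered |
|---|---|---|
| Sensors prompting more walking | Walking while wearing sensors | Inpatient only, since tracking ends at discharge |
| Previous mobility regained | Recovery of mobility, not exercise | From the operation |
| Pushing oneself to exercise | Exercise | From the operation |

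The other five items cover applying the sensors, comfort, pain, quality of life and feelings about oneself. No item, and no instruction on the form, limits an answer to the time after discharge.

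**Does the assigned walking fall inside the recall period, and does it differ by arm?** Yes to both. It starts on the first postoperative day. The assignments are at least 30 minutes per day and one to two laps twice per day. The documents give no lap length or duration, so the difference in minutes cannot be computed.

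**Inpatient share of the recall period.** Share = stay ÷ (stay + days from discharge to questionnaire). The visit times are from section 7, taken as 14, 42 and 90 days. Section 3 gives only a minimum stay of 2 days; stays of 2, 4 and 7 days, counted from the operation, are assumptions.

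| Assumed stay | 2 weeks | 6 weeks | 3 months |
|---|---|---|---|
| 2 days | 2/16 = 12.5% | 2/44 = 4.5% | 2/92 = 2.2% |
| 4 days | 4/18 = 22.2% | 4/46 = 8.7% | 4/94 = 4.3% |
| 7 days | 7/21 = 33.3% | 7/49 = 14.3% | 7/97 = 7.2% |

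These are shares of calendar days. They show how much of the period overlaps with the hospital stay; they do not measure bias.

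**What an overlap could do (illustration only).** Suppose habits after discharge are identical in the two arms, and ward walking moves a share *q* of intervention patients up one category, net of any such shift among controls. Assume an item SD of 1.0 category and a two-sided 0.05 comparison of 40 with 40. The mean shift is *q*, with standard error 1.0 × √(2/40) = 0.224. The chance of a significant result favouring the intervention is Φ(*q*/0.224 − 1.960): about 6.5% for *q* = 10%, 20% for 25% and 61% for 50%, against 2.5% with no shift. The SD, the shifts and the test are all assumptions, and the plan contains no such test.

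**The case against.** **Bias is possible, not shown.** A reader might infer that the item will favour the intervention. The documents do not support that. Patients answer weeks after discharge and may take the question to mean their current behaviour. The item also asks about effort on one's own part, and walking done on request with a nurse in attendance may not strike patients as that. This objection stands: the wording admits ward walking, but nothing shows that patients will count it.

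**Controls walk too.** Their laps fall in the same period and could raise their answers as well. This stands, and it means only the difference in assigned walking can distort the comparison.

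**The overlap can be small.** At 3 months it is about 2% to 7% for the assumed stays, and the largest shares need a long stay and the earliest visit. This also stands. Because the completion time is not fixed, however, the early visit cannot be set aside.

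**Improvement can still be judged.** A reader might infer that, with no pre-surgery version of the item, improvement cannot be assessed at all. That goes too far. Section 3 admits only people without a regular exercise regimen, and allocation is randomised 1:1, so a comparison between arms after surgery is informative without a baseline copy.

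**The stakes are low.** The endpoint is one of several subjective secondary ones, and no test is planned for it. That limits the weight of the point but does not remove the mismatch between item and endpoint.

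**Conclusion.** The point holds as a mismatch between an endpoint and its only measure. The endpoint concerns the time after discharge; the item also covers the hospital stay, in which the arms are assigned different walking, and the plan has no means of separating the two. A between-arm difference on the item can therefore partly reflect the intervention itself.

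The overlap runs from about 2% of the recall period (2-day stay, 3 months) to about 33% (7-day stay, 2 weeks), given the assumed stays. The size of any resulting bias cannot be derived from the documents, and its direction, though plausibly towards the intervention, is not established. The matter is confined to one minor secondary endpoint; the mobility and complication analyses in section 16 are untouched.

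**What to change.** Reword the item to *Since you left the hospital, how often have you exercised?* and compare the answers between the randomised arms. The inpatient share of the recall period then becomes 0% at every visit, and the existing Never-to-Always scale still fits. Section 9 says that only the last three questions come from a published source. This item is the fifth of eight, so rewording it alters no borrowed wording. The cost is one line on a form at a contact already planned, with whatever approval a change of form needs.

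Section 9 also provides for "assessment of their baseline physical activity before the surgery, using validated questionnaires in the clinic". Repeating that assessment at follow-up is optional. The questionnaires are not named and their recall period is not given, so the documents do not show whether they would suit patients soon after surgery or how long they would take.
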